### 19.5. OBSERVATIONAL ENDPOINTS

- Device Success: Successful deployment of the Tack implant(s) at the intended target site(s) and successful withdrawal of the delivery catheter from the introducer sheath.
- Target Lesion Success: Demonstrated target lesion patency [ $<30\%$  residual diameter stenosis (DS), by visual estimate] without the use of a bailout stent within the target lesion upon completion of the index procedure. This will be assessed for all lesions treated with a Tack implant. In addition, target lesion success will also be analyzed by lack of bailout stent to tacked segment only. Multiple target lesions treated as one lesion with PTA will be analyzed as one lesion.
- Procedural Success: Demonstrated target lesion patency ( $<30\%$  residual DS, by visual estimate) without the use of a bailout stent within the target lesion and without the occurrence of MALE+POD upon completion of the index procedure
- Amputation-free survival (AFS): Freedom from above-ankle target limb amputation or all-cause death at 6 and 12 months
- Freedom from MALE at 12 months + POD at 30 days
- Target lesion(s) tacked segment(s) patency at 12 months defined as the presence of blood flow using duplex ultrasound.
- Target Limb Salvage defined as freedom from any above-ankle target limb amputation at 12 months
- Assisted primary target lesion Tacked segment patency (flow vs. no flow) at 6 and 12 months
- Secondary target lesion Tacked segment patency (flow vs. no flow) at 6 and 12 months
- PSVR patency at 6 and 12 months [Freedom from binary restenosis defined as Peak Systolic Velocity Ratio (PSVR) of  $\geq 2.5$  and/or angiographic percent diameter stenosis of  $\geq 50\%$ ] assessed for the following:
  - Target Lesion(s), defined as the entire contiguous arterial segment treated with angioplasty, inclusive of an additional proximal and distal margin of 5 mm
  - Tacked Segment(s), defined as the Tack device and 5 mm of artery proximal and distal to each Tack. If Tacks are within 10 mm of each other, they will be considered as a single tacked segment for the purposes of this patency assessment.
- Clinically-driven target lesion revascularization (CD-TLR) through 6 and 12 months
- Clinically-driven target vessel revascularization (CD-TVR) through 6 and 12 months

- All-cause death through 6 and 12 months
- Any Target vessel revascularization (TVR) through 6 and 12 months
- Any Target lesion revascularization (TLR) through 6 and 12 months

In addition, the following observational endpoints will be assessed at various time points through 36 months (See Time and Events Schedule **Section 8.1**):

- Changes in Wound, Ischemia, and foot Infection (WIFI) Classification
- Changes in ankle brachial index (ABI) and toe brachial index (TBI)
- Changes in Rutherford Classification
- Changes in the EQ-5D-3L quality of life questionnaire
- Changes in the Walking Impairment Questionnaire (WIQ)
- Tack implant Integrity via X-ray (only performed at 12-month visit)
- Progress of wound(s) present at study entry (healed, improved, unchanged, worsening, amputated)
- Appearance of new wound(s) after study entry
- Unplanned below-ankle target limb amputation(s): digit or transmetatarsal

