**Table 4. TOBA-BTK Trial Baseline Clinical Assessment of Target Limb**

Parameter	Safety Sample N = 35	Performance Sample N = 32
Target Limb		
Left	40.0% (14 / 35)	34.4% (11 / 32)
Right	60.0% (21 / 35)	65.6% (21 / 32)
Number of Patent Tibial / Peroneal Vessels in the Target Limb		
1	42.9% (15 / 35)	46.9% (15 / 32)
2	42.9% (15 / 35)	37.5% (12 / 32)
3	14.3% (5 / 35)	15.6% (5 / 32)
ABI treated leg (mean ± stdev) (minimum, median, maximum)	0.95 ± 0.42 (35) (0.0, 0.94, 1.9)	0.91 ± 0.41 (32) (0.0, 0.93, 1.9)
TBI treated leg (mean ± stdev) (minimum, median, maximum)	0.49 ± 0.30 (24) (0.0, 0.47, 1.1)	0.47 ± 0.28 (23) (0.0, 0.46, 1.1)
Subject Pain Symptoms for Target Limb (check all that apply)		
No Leg Pain	48.6% (17 / 35)	46.9% (15 / 32)
Rest pain	28.6% (10 / 35)	28.1% (9 / 32)
Pain on exercise	28.6% (10 / 35)	31.3% (10 / 32)
Rutherford Clinical Category for Target Limb		
4	11.4% (4 / 35)	12.5% (4 / 32)
5	88.6% (31 / 35)	87.5% (28 / 32)

The mean pre-PTA percent diameter stenosis per lesion was 72.3%± 17.4 and 73.0%± 17.8, for the safety and performance samples, respectively. Total occlusion comprised eight of the lesions (22.2% safety sample, 24.2% performance sample). Of all dissections reported (Safety Sample), the most frequently reported worst dissection grade was B (40.5%) followed by A (35.7%), C (19.0%), and D (4.8%). The worst post-PTA dissection grades pre-Tack at Tack sites were A (21.2%), B (60.6%), and C (18.2%). The mean number of Tack implant(s) used in the Performance Sample was 2.8±2.0 with a range of 1 to 12 per lesion. Tack implant(s) were successfully delivered in 33/36 (91.7%) lesions. Three individual lesions in three subjects were not successfully treated as in each case, the catheter was not able to be advanced to the lesion location. Of the successfully placed Tack implant(s), the post-Tack implant dissection grade was 0 in 32/33 (97.0%) and B in 1/33 (3.0%). Tack implant locations to treat the dissections included anterior tibial artery (32.6%), tibio-peroneal trunk (30.4%), peroneal artery (20.7%), and posterior tibial artery (16.3%). In greater than 89.7% of the Performance Sample vessels, the Tack was placed on the proximal edge of the dissection being treated and in 76.9% of the vessels the Tack was placed on the distal edge of the dissection.

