Device success, which was defined as the ability to successfully deliver and deploy the Tack implant(s) to the intended target sites was successfully achieved in 32/35 (91.4%; 95% CI 77.6, 97.0) subjects. In all three subjects where device success was not achieved, the physician was unable to advance the device to the desired position due to tortuous vessel anatomy and/or torque transmission in the delivery catheter. Procedure Success was defined as demonstrated

vessel patency as reported by the physician (visual estimate) without occurrence of MALE + POD on the date of procedure. Procedure success was achieved in 34/35 (97.1%; 95% CI 85.5, 99.5) subjects in the Safety Sample and 31/32 (96.9%; 95% CI 84.3, 99.5) in the Performance Sample. These data support that the Tack device performed as intended in this subject cohort.

ABI was significantly ( $p < 0.05$ ) improved at all time points. At all post-procedure time points there was a significant ( $p < 0.05$ ) in audible Doppler signal. Specifically, at 12 months, 10/34 lesions improved, 23/34 had no change, and 1/34 was worse.

**Table 5** below summarizes amputation-free survival, survival, freedom from amputation, freedom from clinically driven TVR, and freedom from clinically driven TLR for all subjects. At 12 months, the amputation free-survival rate was 84.5% (95% CI; 66.6, 93.2) and freedom from clinically driven TVR and TLR was 93.5% (95% CI; 76.6, 98.3).

**Table 5. Summary for Amputation-Free Survival, Survival and Freedom from Amputation, Clinically Driven Target Vessel Revascularization and Clinically Driven Target Lesion Revascularization in All Enrolled Patients**

Parameter	30 Days	3 Month	6 Month	12 Month
Amputation-free survival, composite of death/amputation	100%	93.8%	93.8%	84.5%
Survival	100%	97%	97%	97%
Freedom from amputation of the limb (above the ankle)	100%	96.8%	96.8%	87.1%
Freedom from clinically driven target vessel revascularization (TVR)	100%	100%	93.5%	93.5%
Freedom from clinically driven target lesion revascularization (TLR)	100%	100%	93.5%	93.5%

Primary patency was defined post-hoc as presence of a Doppler signal, freedom from clinically driven target lesion revascularization (CD-TLR) and major amputation (above the knee). Primary patency was determined per patient and per vessel. Primary patency is lost at the first occurrence of CD-TLR, major amputation or lack of an audible signal observed at the 1, 3, 6 or 12 month follow-up.

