- If the target vessel is the P2 and/or P3, any 1 of the 3 distal arteries must show respective outflow.
- If the target vessel is the TPT, then respective outflow for either the peroneal artery or posterior tibial artery must be confirmed.

**Note:** Normal terminal branching and/or reconstitution of run-off vessels as described above should be confirmed prior to PTA treatment of the target lesion(s) as well as after PTA treatment to the target lesion(s) (prior to Tack deployment)

7. Patent (<50% DS by visual estimate) arterial inflow from aortic bifurcation to the distal edge of the proximal popliteal artery (P1) at the superior end of the patella.

**Note:** Treatment of inflow artery lesions within the iliac (ipsilateral or contralateral), common femoral, superficial femoral, and/or the proximal popliteal (P1) artery(ies) is allowed during the index procedure but must have documented success (<30% residual DS and no major vascular complications) prior to target lesion treatment.

**Note:** If an inflow lesion requires treatment with atherectomy or requires surgical intervention, the patient should not be enrolled

8. After PTA treatment, the target lesion has <30% residual DS and presence of at least one post-PTA dissection (by visual estimate) that the Investigator would otherwise treat by means such as but not limited to additional angioplasty, with longer inflation time or stenting
9. No evidence of aneurysm or acute thrombus in target vessel

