#### 13.3.1. ENROLLMENT (INTENT-TO-TREAT)

A subject is defined as an intent-to-treat (ITT) and officially enrolled in the study once the Tack Endovascular System is advanced through the introducer sheath. Subjects in whom at

least one Tack implant is not placed, will be exited after 30 days. Subjects in whom at least one Tack implant is placed will be followed for 36 months.

In addition, the per-protocol (PP) population will be defined as ITT subjects with evaluable data that have met the definition for device success, excluding subjects with major deviations such as:

- A major inclusion/exclusion criterion deviation; or
- A major procedural deviation

The criteria for deviations meeting the classification of “major” will be defined by an independent designee before study endpoint data is available for statistical analysis.

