Type E	Persistent luminal filling defect with delayed run-off of the contrast material in the distal lumen.
Type F	Filling defect accompanied by total occlusion.
Drug-Coated Balloon (DCB)	Drug-coated balloon catheter used for percutaneous transluminal (balloon) angioplasty.
Duplex Ultrasound (DUS)	A form of medical ultrasonography that includes the following elements on the same screen (“duplex”) to facilitate interpretation 1) B-mode, pulsed Doppler display to visualize the structure within a vessel and 2) Color-Doppler display to visualize the blood flow and hemodynamics within a vessel.

Term	Definition
DUS Flow / No Flow	
DUS Flow - Visualization of color Doppler and pulsed Doppler detectable flow within an arterial segment
 
DUS No Flow – Absence of color Doppler and pulsed Doppler detectable flow within an arterial segment with evidence of flow within the corresponding venous segment

Index Procedure	The interventional procedure during which the study device is advanced through the introducer sheath and the subject is enrolled.
Intent-to-treat (ITT) subjects	A subject is defined as an intent-to-treat (ITT) patient and officially enrolled in the study once the Tack Endovascular System is advanced through the introducer sheath.
Lesion Success	Demonstrated target lesion patency (<30% residual DS, by visual estimate) without the use of a bailout stent. This will be assessed for all lesions treated with a Tack. In addition, target lesion success will also be analyzed by lack of bailout stent to tacked segment only. Multiple target lesions treated as one lesion with PTA will be analyzed as one lesion.
Limb Salvage	Freedom from any above-ankle target limb amputation
Major Adverse Event (MALE)	Above-ankle target limb amputation or major re-intervention to the target lesion(s) (defined as new bypass graft, jump/interposition graft revision, or thrombectomy / thrombolysis)
Major Re-intervention	New bypass graft, jump/interposition graft revision, or thrombectomy / thrombolysis occurring after the index procedure
Major Amputation	Any above the ankle amputation to the target limb.
Minor Amputation	Any below the ankle amputation to the target limb (digital or transmetatarsal (ray or complete))

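### Procedural Success can be met with no Tack placed and Target Lesion Success omits lesions the device could not reach, so only Device Success fully counts non-delivery

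*Combined protocol and SAP*

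**What the plan says.** Three acute endpoints are listed in the synopsis and in Sections 6.3, 19.5 and 24.

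- **Device Success:** "Device Success: Successful deployment of the Tack implant(s) at the intended target site(s) and successful withdrawal of the delivery catheter from the introducer sheath". It fails when no Tack is deployed.
- **Target Lesion Success:** under 30% residual stenosis by visual estimate and no bailout stent in the target lesion at the end of the procedure. On its denominator the plan says: "This will be assessed for all lesions treated with a Tack implant".
- **Procedural Success:** the operator must read the residual stenosis as under 30%, and the subject must finish "without the use of a bailout stent within the target lesion and without the occurrence of MALE+POD upon completion of the index procedure". No denominator is given and delivery of a Tack is not a component.

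Two other provisions matter. Angiographic inclusion criterion 8 (Section 7.4.2) reads "After PTA treatment, the target lesion has <30% residual DS and presence of at least one post-PTA dissection (by visual estimate"), and it applies before the device is used. Under Section 13.3.1 a subject is "officially enrolled in the study once the Tack Endovascular System is advanced through the introducer sheath". Enrolled subjects with no Tack are therefore foreseen; Sections 7.3 and 13.3.1 have them exit after 30 days.

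Section 19.2 assigns the ITT population to the primary and secondary endpoints. Section 19.8.4 says only that observational endpoints are summarised descriptively.

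**The concern.** The device has one acute task: to be delivered to a dissection and repair it. An acute success rate would be expected to fall when delivery fails.

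Procedural Success need not fall. If the catheter cannot reach the lesion and nothing further happens, the end-of-procedure stenosis is the PTA result that qualified the subject for entry. The endpoint then credits balloon angioplasty alone.

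Target Lesion Success has a separate problem, which lies in its denominator. A lesion the device cannot reach is not a Tack-treated lesion and is not scored. That holds even if it then receives a bailout stent, a use Section 13.5 foresees when the Tack cannot treat a persistent flow-limiting dissection.

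The stake is a favourable bias in two reported acute rates of a study that Section 16.3 says will support a premarket approval application.

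**Working it through.** **Inputs (Section 4.2, TOBA-BTK feasibility study).** 35 subjects were enrolled, 32 received a Tack, and in 3 the catheter could not reach the site. Device success was 32/35. "Procedure success was achieved in 34/35 (97.1%; 95% CI 85.5, 99.5) subjects in the Safety Sample", and it was 31/32 among subjects with a Tack. "Tack implant(s) were successfully delivered in 33/36 (91.7%) lesions". Planned enrolment here is 232 (Section 19.6). The plan states no expected rate for any acute endpoint.

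**1. Reproducing the stated figures.** The Wilson score 95% interval is [p + z²/2n ± z√(p(1−p)/n + z²/4n²)] / (1 + z²/n), with z = 1.96.
- 32/35 = 91.4% (77.6, 97.0): matches.
- 34/35 = 97.1% (85.5, 99.5): matches.
- 31/32 = 96.9% (84.3, 99.4): the plan prints 99.5 as the upper limit, a rounding difference.

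**2. How subjects without a Tack were scored.** Successes: 34 − 31 = 3. Subjects: 35 − 32 = 3. All 3 counted as procedure successes, which is why procedure success (97.1%) exceeds device success (91.4%) by 5.7 points.

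**3. Requiring delivery.** The three subjects without device success are the three without a Tack, so requiring Device Success or a placed Tack gives the same figure: 31/35 = 88.6% (Wilson 74.0, 95.5). The drop is 3/35 = 8.6 points.

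**4. Lesions.** 36 − 33 = 3 lesions were not reached (3/36 = 8.3%). Over Tack-treated lesions the success rate could reach 33/33 = 100%. Over attempted lesions it cannot exceed 33/36 = 91.7% (Wilson 78.2, 97.1).

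**5. Carrying the rate to this trial (assumption).** 232 × 3/35 = 19.9, so about 20 subjects with no Tack. The Wilson limits of 32/35 imply non-delivery of about 3.0% to 22.4%; applied unrounded to 232 they give 6.9 to 51.9, or 7 to 52 subjects.

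**6. Response of the endpoint to non-delivery.** Let d be the non-delivery rate and s the success rate among delivered subjects, here s = 31/32. If no undelivered subject fails for another reason, Procedural Success as written is s(1 − d) + d. With delivery required it is s(1 − d).

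| d | As written | Delivery required |
|---|---|---|
| 3.0% | 97.0% | 94.0% |
| 8.6% | 97.1% | 88.6% |
| 22.4% | 97.6% | 75.2% |

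The written rate stays near 97% whatever d is. If a fraction b of undelivered subjects fail anyway, for example through a bailout stent, the gap is d(1 − b). At d = 8.6% it therefore lies between 0 and 8.6 points.

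**The case against.** **Device Success already reports non-delivery.** This is correct. Tacks deployed and catheter withdrawal are also recorded (Section 13.3.3), and device events are reported (Section 18). A reader might infer that the plan conceals delivery failures. It does not, and the feasibility study reported them openly as 32/35 subjects and 33/36 lesions.

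**Procedural Success is not automatic.** Also correct. Stenosis is read at completion, so a later loss of result, a bailout stent or a MALE+POD event fails the subject. An unreached lesion that is stented drops out of Target Lesion Success but fails Procedural Success. What stands is the unstented, undelivered subject whose PTA result holds.

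**The denominator is unstated, so a false success is not proven.** This is fair. Section 13.4.2 names final residual stenosis only for Tack-treated lesions, in a list that is not exhaustive. For a subject without a Tack, the value might be missing or might default to the entry reading. That ambiguity is itself a reason to specify.

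**The feasibility definition differed.** It required physician-read patency and no MALE+POD on the procedure date, with no 30% limit and no stent clause. Its figures illustrate the missing delivery requirement, which both definitions share, but do not predict this trial's rates.

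**Two further inferences are not supported.**
- A reader might call the limb-event component empty because Section 24 defines major re-intervention as "New bypass graft, jump/interposition graft revision, or thrombectomy / thrombolysis occurring after the index procedure". Section 17.5 carries no such limit, and death and above-ankle amputation still count.
- A reader might say the visual estimate must give way to the core laboratory's. The plan specifies visual estimate by choice, and Section 21.9 already sends all angiograms for central reading.

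**Conclusion.** The point holds in a limited form. Two of the three acute endpoints do not fully reflect non-delivery, for two separate reasons: Procedural Success lacks a delivery requirement and scores a stenosis threshold already met at entry, and Target Lesion Success excludes lesions not treated with a Tack. The entry criterion does not explain the second.

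On the feasibility figures, the effect is up to 8.6 points on Procedural Success and 8.3 points on the ceiling of Target Lesion Success. The estimate of about 20 affected subjects assumes that 3/35 carries over; the number miscounted would be smaller if some of them fail for other reasons.

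A reader might infer that the trial's conclusions are at risk. They are not: the endpoints are observational and descriptive, carry no hypothesis, and play no part in study success (Sections 19.8.4, 19.12, 19.13). Alpha and power are unchanged. This is a cheap improvement to how acute results are reported.

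**What to change.** 1. In the synopsis and Sections 6.3, 19.5 and 24, define Procedural Success over all ITT subjects and add Device Success to the existing components. Also show the result by Tack placed, yes or no. State Device Success at subject level so that it can serve as a component.
2. In the same places, report Target Lesion Success over all target lesions in which Tack delivery was attempted, counting non-delivery or a bailout stent as failure. Keep the rate over Tack-treated lesions as supportive.
3. In Section 13.4.2, record final residual stenosis for every target lesion in which delivery was attempted.

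Deployment, withdrawal and bailout-stent data are already collected (Sections 13.3.3 and 13.4.2). The cost is wording, one case report form clarification and table programming. The downside for the sponsor is less favourable acute rates.

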#### 19.6. SAMPLE SIZE

The sample size for the primary efficacy endpoint of freedom from MALE at 6 months plus POD at 30 days was calculated using a one-sided, single group, normal approximation test of a proportion (with continuity correction) against a performance goal. The performance goal for this endpoint is 74% developed based on the information reported in table VIIb and figure 2A of Conte (2009). From figure 2A, the estimated 6-month rate of freedom from MALE + POD in the infra-popliteal group is 80.5% with 95% confidence interval calculated to be (77%, 84%). Applying the recommended 3% margin to the lower bound of the confidence interval yields the 74% OPG. Assuming the observed freedom from MALE+POD is 84% and a one-sided Type I error rate of 0.025, a sample size of 186 subjects provides 90% power to detect this difference between observed freedom from MALE+POD and the performance goal of 74%.

The sample size for the primary safety endpoint of MALE+POD at 30 days was calculated using the exact binomial distribution. This is also a one-sided, single group test of a proportion against a performance goal. The performance goal for this endpoint was established at 12%. This performance goal was derived from the information reported in table VIIa of Conte (2009). In that table, MALE+POD was not reported, however MALE and 30-day death were reported separately. The sum of those two estimates (8.9%) was used for sample size calculation. Conte (2009) established performance goals for safety endpoints by constructing a 95% confidence interval and using the upper bound of that interval as the performance goal. With some algebraic manipulation, a similar 95% confidence interval was established for the 8.9% point estimate of 30day MALE+POD which resulted in an upper bound of 11.9%. Therefore 12% is used as the performance goal for this endpoint. Assuming an observed MALE+POD rate of 5%

 Joseph L. Mills, Sr, MD, [name], David G. Armstrong, DPM, MD, PhD, [name], [name], [name], MPH, and [name], on behalf of the Society for Vascular Surgery Lower Extremity Guidelines Committee, The Society for Vascular Surgery Lower Extremity Threatened Limb Classification System: Risk stratification based on Wound, Ischemia, and foot Infection (WIFI). J Vasc Surg. 2014; Volume 59, Issue 1, Pages 220–234.e2

and a one-sided Type I error rate of 2.5%, a sample size of 171 subjects provides 90% power to demonstrate that the observed 30-day MALE+POD rate is below the performance goal of 12%.

Since the required sample size for the primary efficacy endpoint (186), is larger than the required sample size for the primary safety endpoint (171), an effective sample size of 186 subjects meeting the ITT definition will be assumed. Assuming approximately 20% loss to follow-up, total enrollment will be  $186/0.80$  or 232 subjects.

The secondary endpoint of primary patency of the tacked segment of the treated lesion at 6 months will also be formally tested against a performance goal of 64%. The performance goal of 64% was chosen as a result of a meta-analysis combining 13 papers that reported 6-month patency for standard PTA or from which the 6-month patency rate could be derived. These papers covered several patient populations, however all these populations are target populations for use of the Tack. A meta-analysis was performed on the results reported in these papers and the random effects estimate of 6-month patency was 63.5%. Therefore, 64% was chosen as the performance goal. Assuming an observed 6-month patency rate of 81% and a one-sided Type I error rate of 2.5%, the effective sample size given above for the primary efficacy endpoint of 175 would provide greater than 90% power to detect the difference between an observed 6-month patency of 81% and the performance goal of 64%.

